5.2.3 Safety Population

Will be the same as the ITT population.

5.2.4 Pharmacodynamic Evaluable Population

The pharmacodynamic population will include all treated patients for whom pre- and post-infusion pharmacodynamic data are available.

5.2.5 Pharmacokinetic Analysis Population

The PK population will include all treated patients for whom at least one pharmacokinetic sample is quantified.

5.3 General Principles for Presenting Study Data

All statistical analyses will be performed at SDS using SAS® (Version 9.3 or higher, SAS Institute Inc., Cary, NC, USA). All statistical analyses will be performed after this SAP is finalised and approved and the study database is locked.

Continuous data will be summarized using descriptive statistics where the following parameters will be reported:

- Number of observations (n),
- Mean,
- Median,
- Standard deviation (SD),

- Range (Min, Max)

Categorical data will be presented as the number and percentage of patients.

Time to event endpoints defined in Section 4.2.3 (e.g. duration of response, OS and time to iCPD) will be analysed using Kaplan-Meier methods taking censoring into account. The Kaplan-Meier plot and corresponding estimate of the median value with 95% confidence interval will be reported.

All tests will be one-sided and performed at the 5% significance level. When reporting the results of significance tests, p-values will be reported together with 2-sided 90% confidence intervals.

Throughout the report, the number of decimal places given for the summary statistics; mean, STD, confidence interval and median values will exceed that of the source data by one. Minimum and maximum will have the same number of decimal places as the source data. For relative frequencies, integer with one decimal and %-sign will be presented and for p-values four (three) decimals will be reported.

Percentages will be based on number of patients with data at a certain time point with the exception of presentations of medical history, medications and AEs where the percentages will be based on the number of patients in the study population.

In general, all data will be listed, sorted by phase of study, cohort and patient, and when appropriate by cycle within patient. All summary tables will be structured with a column for cohort and will be annotated with the total population size relevant to that table/cohort, including any missing observations. Summary tables will include summaries for visits for Cycle 1 (Screening, Day 1 pre dose, Day 1 post dose, Day 8 pre dose, Day 8 post dose and Day 22 End of Cycle 1 as appropriate) whereas subsequent cycles will be summarized with summary statistics for the minimum and maximum observed value during the subsequent cycles.

The two phases of the study will be summarized separately. In addition, cohorts from phase 1 and phase 2 may be combined and summarized if appropriate.

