- 6 Serum chemistry will be performed at screening (within 10 days of Cycle 1 Day 1) and on Days 1 and 8 of every cycle beginning with Cycle 1 Day 1. Chemistry panel is to include the following parameters: lipase, amylase, albumin, total protein, blood glucose (non-fasting), sodium, potassium, chloride, bicarbonate, magnesium, calcium, blood urea nitrogen (BUN), creatinine, AST, ALT, alkaline phosphatase (ALP), total bilirubin, direct bilirubin, lactate dehydrogenase (LDH), gamma glutamyltransferase (GGT), and phosphate. If screening chemistry is performed within 72 hours of Cycle 1 Day 1, the sample does not need to be repeated. Thyroid function testing includes triiodothyronine (T3) or free triiodothyronine (FT3), Thyroxine (T4) or free thyroxine (FT4), and TSH
- 7 Hematology will include CBC and differentials. Hematology will be performed at screening (within 10 days of Cycle 1 Day1) and on Days 1 and 8 of every cycle beginning with Cycle 1 Day 1. If screening hematology is performed within 72 hours of Cycle 1 Day 1, the sample does not need to be repeated
- 8 Urinalysis will be performed at screening and on Day 1 of every 21-day cycle. If screening urinalysis is performed within 72 hours of Cycle 1 Day 1, the sample does not need to be repeated
- 9 For women of child bearing potential, a serum pregnancy test must be performed at screening only. Urine or serum pregnancy tests must be done within 72 hours before the first dose of study drug. A urine pregnancy test can be performed at all other study visits. Monthly pregnancy testing should be conducted as per local regulations where applicable.

- 10 The adverse event reporting period is from the time the patient signs consent until 30 days after study-drug discontinuation. Adverse events that lead to study-drug discontinuation should be followed until resolution or stabilization.
- 11 Pembrolizumab 200 mg will be administered first on Day 1 of each 21-day cycle.
- 12 All patients will be required to be administered All patients will be required to be administered 800 mg of ibuprofen (or equipotent and equivalent alternative NSAID) prior to administration of birinapant on Day 1 and Day 8 as prophylaxis for possible events of cranial nerve palsy associated with the administration of birinapant.
- 13 Birinapant will be administered 30 minutes (+10 minutes) after pembrolizumab on Day 1 and by itself on Day 8 of each 21-day cycle.

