12.6 Analysis of Safety Data

The safety and tolerability of pembrolizumab and birinapant will be based on results of DLT incidence, reported SAEs, AEs, vital sign measurements, physical examinations, clinical laboratory information, ECOG performance status, and concomitant medications. Exposure to study drug and reasons for discontinuation will be tabulated. These data will

be summarized descriptively for the dose escalation phase and for the dose expansion phase of the protocol separately for the ITT population. Safety data will be summarized descriptively by cohort and also summarized descriptively over cohorts within each of the two phases of the protocol.

For parameters measured over time, data and changes from baseline will be summarized for each time point. Adverse events will be coded using the current *Medical Dictionary for Regulatory Activities* (MedDRA) classification system, and will be summarized by system organ class and preferred term.

Additional safety analyses may be determined in order to most clearly describe toxicity rates and to further define the safety profile of pembrolizumab and birinapant.

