Clinical Laboratory Tests (hematology, clinical chemistry, immunology, serology, urinalysis, pregnancy testing and histology) will be summarized regarding observed values, change from baseline and abnormal findings in accordance with Section 5.3 by cancer cohort and in total over cohorts. In addition, the categorization of the observed values into 'low', 'normal' and 'high' will be summarized in max/min shift from baseline tables by cohort and in total over cohorts. There will be two variants of each shift table, one where the max/min is taken over the samples taken after the first dose but before the 2nd dose and one where the max/min is taken over all samples taken after the first dose.

5.7.3 *Physical Examination*

Physical examination will be presented as the number and percentage of patients with normal, abnormal not clinically significant, abnormal clinically significant result over time by Body System and cancer cohort.

Findings that are present during screening and prior to drug administration will be included under Medical History. Significant findings made after drug administration that meet the definition of an AE will be reported under the AE section.

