5.7.4 Vital Signs

Vital signs will be summarized regarding observed values and change from baseline in accordance with Section 5.3 by cancer cohort and in total over cohorts.

In case several measurements are taken for the same planned sample time, average values will be used.

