5.7.5 Electrocardiogram

ECG results will be summarized regarding observed values, change from baseline values and findings (normal, abnormal not clinically significant and abnormal clinical significant) in accordance with Section 5.3 by cancer cohort.

If one of the measurements within a triplicate ECGs is classified as abnormal the value for that visit is classified as abnormal.

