5.9 Changes to Planned Analysis

The statistical analysis of the primary endpoint has been supplemented with how the analysis will be done in case of the number of patients evaluable for efficacy differs from the planned number of patients in the Simon's design.

6. References

BPT-201 v4.0/incl amendment 03, final version dated 18 January 2018.

Imaging Review Charter for BPT-201, MEDIAN Technologies, 7 February 2018.

Simon R. Optimal two-stage designs for phase II clinical trials. *Controlled Clinical Trials.* 1989; 10(1):1–10. [PubMed: 2702835]

Statistical Principles for Clinical Trials (ICH Topic E 9). EMEA. September 1998, CPMP/ICH/363/96.

7. Appendix 1

Table 5 Schedule of Study Procedures and Assessments

Study Procedures	Screening (Within 28 Days of Cycle 1 Day 1)	Cycle 1			Subsequent Cycles		End of the Third Week of Every Third 21- Day Cycle	Every six weeks	Every 12 weeks	Follow up		
		Day 1	Day 2	Day 8	Day 1	Day 8				Safety Follow up Visit (30 Days After Study Drug Discontinuation)	Progressive Disease/ Study Drug Discontinuation ²⁰	Overall Survival Follow-up ²¹
Visit Window				± 2 Days		± 2 Days	± 3 Days			+7 Days	± 3 Days	
Informed Consent	X											
Inclusion/ Exclusion Criteria	X											
Demographics	X											
Medical History and Disease Characteristics ¹	X											
ECOG Performance Status	X	X			X					X	X	
Serology ² (HSV, VZV)	X											
Review Prior/ Concomitant Medications	X	X		X	X	X				X		
Measurement of Vital Signs ³	X	X		X	X	X				X		
Physical Examination	X	X			X					X		
Weight and Height ⁴	X	X			X							

Study Procedures	Screening (Within 28 Days of Cycle 1 Day 1)	Cycle 1			Subsequent Cycles		End of the Third Week of Every Third 21- Day Cycle	Every six weeks	Every 12 weeks	Follow up		
		Day 1	Day 2	Day 8	Day 1	Day 8				Safety Follow up Visit (30 Days After Study Drug Discontinuation)	Progressive Disease/ Study Drug Discontinuation ²⁰	Overall Survival Follow-up ²¹

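### After Cycle 1 the SAP summarizes laboratory, vital-sign and ECG data only as per-patient minimum and maximum, against the protocol's per-time-point summaries, and these extremes depend on time on treatment

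*SAP*

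**What the plan says.** Protocol 12.6, on safety data: "For parameters measured over time, data and changes from baseline will be summarized for each time point".

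SAP 5.3 gives visit-level summaries for Cycle 1 (screening, Day 1 and Day 8 before and after dosing, end of cycle), "whereas subsequent cycles will be summarized with summary statistics for the minimum and maximum observed value during the subsequent cycles".

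The rule reaches all three data types by cross-reference:
- Laboratory tests (SAP 5.7.2) "will be summarized regarding observed values, change from baseline and abnormal findings in accordance with Section 5.3 by cancer cohort".
- SAP 5.7.4: "Vital signs will be summarized regarding observed values and change from baseline in accordance with Section 5.3 by cancer cohort".
- SAP 5.7.5: "ECG results will be summarized regarding observed values, change from baseline values and findings"; that sentence also points to Section 5.3.

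The laboratory shift tables in SAP 5.7.2 are built on extremes too. One variant is limited to samples before the second dose, and there is "one where the max/min is taken over all samples taken after the first dose".

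SAP 5.4.2.1 defines change from baseline as the value at a given visit minus the baseline value, and gives no rule for an extreme taken over several visits. SAP 5.9 declares a single change: "The statistical analysis of the primary endpoint has been supplemented with how the analysis will be done" when the evaluable number differs from plan. It does not mention safety summaries.

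**The concern.** Three things follow from these passages.

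- The SAP does not deliver the summaries that the protocol promises, and does not say so.
- A table of change from baseline for the minimum and maximum cannot be programmed without a definition that the SAP lacks.
- The expected maximum of repeated noisy readings rises with their number, and the expected minimum falls. A patient treated longer has more readings, so part of what these rows show reflects exposure time. The trial is single-arm, so no control group shows how large that part is.

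At stake is the description of safety. The magnitude of clinically significant laboratory changes, the pattern of laboratory shifts that might suggest a trend, and vital-sign and ECG findings are primary endpoints in the escalation phase (Protocol 3.4.1.1) and in the various solid tumors cohort (Protocol 3.4.2.1). One row pooled over all later cycles cannot show a trend.

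Thyroid function is the clearest case. It is tested at screening and then every six weeks, and SAP 4.3.2.1 places it in clinical chemistry. All its scheduled on-treatment results therefore fall after the 21-day Cycle 1, and it would have no by-visit on-treatment summary at all.

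**Working it through.** The documents give no figure on this point, so there is none to reproduce. The check asks what the minimum/maximum rows would show if the drugs had no effect.

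**Inputs from the documents**
- Serum chemistry and hematology are taken "on Days 1 and 8 of every cycle beginning with Cycle 1 Day 1" (Protocol Section 6, Table 8 footnotes); the ECG is scheduled on the same days. That is 2 readings per cycle.
- Treatment lasts up to 35 cycles (Protocol 6.1).
- Readings after Cycle 1 for a patient treated for c cycles: k = 2 × (c − 1). This runs from 0 for a patient who stops in Cycle 1 to 2 × 34 = 68.

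**Assumptions, not in the documents**
- Each patient's readings are normal and stable, in units of the within-patient SD.
- Visit-to-visit autocorrelation is 0, 0.5 or 0.8, shown as a range.

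**Formula.** For independent readings the expected maximum is E[max] = ∫ x · k · φ(x) · Φ(x)^(k−1) dx. Baseline has expectation 0, so this is also the expected distance above baseline. The minimum has the same size with the opposite sign. The autocorrelated cases come from a first-order autoregressive simulation of 40,000 patients.

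| Cycles | k | Autocorrelation 0 | 0.5 | 0.8 |
|---|---|---|---|---|
| 2 | 2 | 0.56 | 0.40 | 0.25 |
| 3 | 4 | 1.03 | 0.82 | 0.56 |
| 6 | 10 | 1.54 | 1.37 | 1.03 |
| 9 | 16 | 1.77 | 1.63 | 1.28 |
| 18 | 34 | 2.10 | 2.00 | 1.71 |
| 35 | 68 | 2.37 | 2.29 | 2.06 |

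**Contrast between groups.** Nine cycles against three gives 1.77 − 1.03 = 0.74 SD with independent readings and 1.28 − 0.56 = 0.72 SD at autocorrelation 0.8. The level depends on the assumed autocorrelation; this contrast hardly does.

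**Vital signs.** Table 8 asks for readings before and after each infusion: 4 on Day 1 and 2 on Day 8, so 6 per cycle. If these are pooled when the extreme is taken, the independent-reading values are 1.63 SD at 3 cycles (k = 12) and 2.23 SD at 9 (k = 48).

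**Shift tables.** If a stable patient has a 2.5% chance of a high value at each sample (assumption, independent samples), the chance of at least one after Cycle 1 is 1 − 0.975^k. That is 9.6% at 3 cycles and 33.3% at 9. The shift table over all samples therefore carries the same dependence.

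**By-visit summary as in Protocol 12.6.** Under the same assumptions the expected mean change is 0 at every visit, whatever the time on treatment. The simulated last-visit mean lay between −0.004 and 0.004 SD for 2 to 35 cycles.

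**The case against.** The case for the SAP is substantial. Protocol 12.1 leaves analysis details to the SAP. The endpoints speak of clinically significant changes and shifts, and worst values address these directly; in small cohorts, by-visit means can average away the one extreme patient. Treatment duration and cycles started are tabulated by cohort (SAP 5.5.6), so differences in exposure are visible. Mock-up tables sit in separate documents, so final layouts are unknown. By-visit means have a weakness of their own: late visits describe only patients still on treatment. All of this supports keeping the worst-value tables. None of it turns them into the summaries promised in Protocol 12.6, and omitting a promised summary goes further than detailing it.

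A reader might infer more than the documents support:
- *That the tables would show a false upward drift over time.* They have no time axis after Cycle 1. The artefact is an outward spread, which appears between patients or groups with different exposure.
- *That onset and recovery are wholly hidden.* The listings keep the data, sorted by cycle within patient where appropriate, and flag abnormal and clinically significant laboratory values. Treatment-emergent adverse events are split into Cycle 1, later cycles and safety follow-up, and physical examination is shown over time. What is missing is a time course in the later-cycle summary tables of laboratory, vital-sign and ECG values.
- *That dose decisions or the efficacy tests are affected.* The escalation rule counts dose-limiting toxicities in Cycle 1, where visit-level summaries remain. Safety analyses are descriptive, and the two-stage response tests do not use these tables.
- *That a shift of more than 2 SD is typical.* With independent laboratory or ECG readings it needs roughly 18 cycles or more. The median progression-free survival figures of about 2 months that the protocol cites for pembrolizumab in ovarian and head and neck cancer correspond to about 61/21 ≈ 3 cycles.

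**Conclusion.** The point holds as a discrepancy between protocol and SAP with a predictable artefact. SAP 5.3 departs from Protocol 12.6 without declaring it in SAP 5.9, and leaves change from baseline undefined for the quantities it tabulates. This rests on the text alone.

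The direction of the artefact held at every autocorrelation tried: more readings push the maximum up and the minimum down. Its size is illustrative. It is about 0.6 to 1.0 within-patient SD at 3 cycles and 1.3 to 1.8 SD at 9 cycles, for autocorrelation 0.8 to 0, assuming stable normal readings and full attendance at scheduled visits. Groups that differ in time on treatment will tend to differ in these rows without any difference in toxicity. The consequence is confined to descriptive safety reporting, but that reporting bears on a primary endpoint in the escalation phase and in the various solid tumors cohort.

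**What to change.** - Add summaries of observed values and changes from baseline by scheduled visit, with n, for Cycle 2 onward, including the six-weekly thyroid tests.
- If a minimum n is used to limit table length, set it so that escalation dose levels, which enroll 3 to 6 patients, are not dropped.
- Add a note that later by-visit means describe only patients still on treatment.
- Keep the minimum/maximum and shift tables as a supplement. Define in SAP 5.4.2.1 how their change from baseline is derived, say whether pre- and post-dose vital signs are pooled, and show the number of readings or cycles behind each row.
- List in SAP 5.9 any departure from Protocol 12.6 that remains.

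The data are already scheduled for collection. The cost is some programming and longer tables.

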5.4 Statistical/Analytical issues

5.4.1 Missing Data and Handling of Dropouts

Missing values will not be imputed/replaced in the efficacy analysis.

Laboratory values which are greater/smaller than a stated value will be replaced by the stated value (for example <1 will be replaced by 1) when summarized in tables.

If the start and/or stop dates for medication, AEs and medical history are unknown the date will be imputed to calculate the duration of AE or to decide if the medication was ongoing at baseline or not. No imputation will be presented in individual patient listings. An unknown date will be imputed as follows:

- If the month and date are unknown, the date will be set to June 30th.
- If the day is unknown, the day will be set to the 15th.
- If the year is unknown, the date will not be imputed.

5.4.2 *Data Transformations and Derived Variables*

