5.6.5 Sensitivity Analyses

A sensitivity analysis of the primary endpoint will be conducted if there are patients that are wrongly included into the study and receives a dose of pembrolizumab and birinapant. In that case, the primary efficacy analysis will be repeated when those patients are excluded from the efficacy evaluable population, for the cohorts it concerns, as a sensitivity analysis. Also other major protocol deviations may be considered in this sensitivity analysis.

5.7 *Safety Analyses*

No formal statistical analyses will be performed, although descriptive summaries for continuous data and for categorical data will be provided in accordance with Section 5.3 if other not stated. Complete listings of all patient safety evaluations will be provided to support each summary table.

All presentations will be based on the safety analysis set.

5.7.1 *Adverse Events*

Adverse Events (AEs) will be coded by system organ class (SOC), preferred term (PT) and Verbatim name using MedDRA Version 20.0

All AEs will be listed whereas the treatment emergent AEs (TEAEs), i.e. any AE with onset or worsening on or after the first dose of any IMP and within 30 days after the last dose of IMP, will be summarized as follows. The number of TEAEs, as well as the number and percentage of patients reporting any TEAE will be summarised for Cycle 1, subsequent cycles and Safety follow-up by cohort. Separate summary tables will be produced for the following:

1. TEAEs related to IMP by Verbatim names
2. TEAEs related to IMP by SOC and PT
3. TEAEs not related to IMP by Verbatim name
4. TEAEs not related to IMP by SOC and PT
5. Serious Adverse Events (SAEs) by Verbatim name
6. SAEs by SOC and PT.
7. TEAEs related to IMP by AE grade
8. TEAEs not related to IMP by AE grade

AEs leading to withdrawals or death will be presented by cohort.

All percentages will be based on the number of patients in the safety set.

5.7.2 *Clinical Laboratory Tests*

All laboratory parameters for individual patients will be listed and patients with abnormal values (out of normal range reported by the laboratory) and with clinically significant abnormalities (according to the Investigator's criteria) will be flagged.

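### SAP 5.4.1 fills in partial AE and medication dates with fixed dates that have no bound at first dose, start or stop, so some imputed dates are impossible

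*SAP*

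**What the plan says.** The rule in SAP 5.4.1 applies "If the start and/or stop dates for medication, AEs and medical history are unknown". It has three branches, none of them conditional:

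- "If the day is unknown, the day will be set to the 15th"
- "If the month and date are unknown, the date will be set to June 30th"
- "If the year is unknown, the date will not be imputed"

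Two uses are named: "the date will be imputed to calculate the duration of AE or to decide if the medication was ongoing at baseline or not". On visibility, the SAP adds "No imputation will be presented in individual patient listings".

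Three other places depend on these dates:

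- SAP 4.1.5 defines a prior medication as one stopped before baseline, and SAP 5.5.5 tabulates prior and concomitant medications separately.
- SAP 5.7.1 lists all AEs but summarizes only treatment-emergent ones, meaning "any AE with onset or worsening on or after the first dose of any IMP" and within 30 days after the last dose. It gives no rule for a partial onset date and does not refer to 5.4.1.
- Protocol 12.1 says that missing data will not be imputed in the safety analyses. SAP 5.9, which lists departures from the protocol's analysis, mentions only the primary endpoint.

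**The concern.** A fixed mid-month or mid-year date ignores what is already known about the patient. For a first dose on the 20th, the 15th of that month lies before treatment. For an AE known to start on the 20th, a stop on the 15th of that month lies before its own start.

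Medication status is the most direct problem, because deciding it is one of the two named uses and its result goes into planned tables. Treatment emergence would matter more if the rule were applied to it. Safety is the primary endpoint of the dose-escalation phase and of the various solid tumors cohort. A dose level has 3 to 6 patients, so one reclassified patient can move a percentage by 1/6 = 17 to 1/3 = 33 points. Imputed dates do not appear in the listings, so such an error would be harder to trace.

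**Working it through.** The SAP gives no figure for this point, so there is none to reproduce. The check applies the rule as written. Duration is taken as stop − start + 1; the SAP gives no formula.

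**Worked cases**

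| Known facts | Imputed date | Result |
|---|---|---|
| First dose 20 Oct, true onset 25 Oct, day unknown | 15 Oct | 5 days before first dose |
| Same, month and day unknown | 30 June | 112 days before first dose |
| AE start 20 Oct, true stop 27 Oct, stop day unknown | stop 15 Oct | −4 days (true value 8) |
| Same, stop month and day unknown | stop 30 June | −111 days |
| True start 3 Oct, start day unknown, stop 8 Oct | start 15 Oct | −6 days (true value 6) |
| Baseline and first dose 20 Oct, medication stopped later in October, day unknown | stop 15 Oct | classed as prior |

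**Onset before first dose, day unknown.** The imputed date precedes first dose only if first dose is after the 15th and onset falls in the same calendar month.

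*Calendar count.* Assume first dose is equally likely on each day of a 365-day year. The number of (first dose, onset) pairs that fail is 136 per 31-day month (16 × 17/2), 120 per 30-day month (15 × 16/2) and 91 in February (13 × 14/2). The total is 7 × 136 + 4 × 120 + 91 = 1,523.

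- Onset uniform over days 0–20: 1,523 / (365 × 21) = 19.9%.
- Onset uniform over days 0–62: 1,523 / (365 × 63) = 6.6%.

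*Model.* Assume 30-day months, first-dose day uniform, and exponential time to onset with mean m, in whole days. Let S(k) be the sum of 1 − exp(−j/m) over j = 1 to k. With m = 15, S(15) = 5.83 and S(30) = 17.46.

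- Among AEs starting in the month of first dose: 5.83 / 17.46 = 33%.
- Among all AEs: 5.83 / 30 = 19%.
- Among AEs within 30 days of first dose: about 22%.

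If m runs from 5 to 30 days, the same-month figure runs from 42% to 30%.

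**Negative duration, stop day unknown.** This happens when the AE starts after the 15th and ends in the same month.

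- Stop 7 days after start: (7 × 9 + 4 × 8 + 6) / 365 = 101/365 = 27.7%.
- Stop 14 days after start: (7 × 2 + 4 × 1) / 365 = 18/365 = 4.9%.
- Exponential length with mean 7 days: S(15) = 9.25 and S(30) = 23.58. That gives 9.25 / 23.58 = 39% of AEs ending in the month they start, and 9.25 / 30 = 31% of all AEs.

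The share depends strongly on length: 40.8% for a stop 3 days after start, 0% for 28 days. If instead the start day is unknown, a stop 7 days later gives a negative duration in 12 × 7 / 365 = 23.0%.

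**Month unknown.** On the calendar count, 47.7% of onsets (days 0–20) or 41.9% (days 0–62) fall before first dose. For a stop 7 days after start, 177/365 = 48.5% give a negative duration.

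**Average bias in duration, day unknown.** With start days uniform over a 30-day month, stop days are uniform too and average 15.5. Imputing 15 therefore shifts mean duration by 15 − 15.5 = −0.5 days when the stop day is unknown, and by +0.5 when the start day is unknown. With mean length 7 days, the −0.5 combines −2.8 days for AEs ending in the month they start and +7.9 days for those that cross into a later month.

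**The case against.** The strongest reply is that the text does not use these dates for treatment emergence. SAP 5.4.1 names AE duration and medication status, SAP 5.7.1 does not point back to it, and Protocol 12.1 rules out imputation in the safety analyses. A reader might infer that the plan as written drops treatment-emergent events from the safety tables. The documents do not support that: it happens only if a programmer also applies the rule to onset. What remains is that 5.7.1 needs an onset date and does not say what to do with a partial one.

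A reader might also infer that AE durations are biased downward overall. They are not: same-month and month-crossing errors nearly cancel.

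Other parts of the reply also stand. None of the AE summary tables named in SAP 5.7.1 reports duration. All AEs are listed, CRF data are monitored and queried, and Protocol 12.1 plans a review of listings for anomalies, so a negative duration might be caught. The higher shares, 33% and 39%, apply only to events within one calendar month.

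The reply does not reach the rule itself. It has no bound, it can give impossible durations, and it can put a medication in the wrong table with no further assumption.

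**Conclusion.** The defect is real and minor. Negative durations and misclassified medications follow from the stated rule alone. Loss of events from the TEAE tables is conditional on a use that the SAP neither states nor excludes.

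The illustrative ranges, about 7–33% for day-unknown onsets and about 5–39% for day-unknown stops, rest on assumed calendar uniformity, onset timing and AE length, and on whether only same-month events are counted; the more extreme inputs shown above go outside them. All are shares of events with partial dates. Without a count of such events, no effect on a safety table can be given. The SAP's imputation of AE dates also sits unreconciled beside the protocol's statement that safety data will not be imputed.

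**What to change.** In SAP 5.4.1:

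- **AE start.** If the known date parts allow onset on or after first dose, impute the later of the default date and first dose, but no later than a known stop date.
- **Stop dates.** Impute no earlier than the start date.
- **Medications.** Treat as concomitant unless the known date parts show that the medication stopped before baseline.
- **TEAE status.** State that an AE with a partial onset date counts as treatment-emergent unless the known parts, including any stop date, show onset before first dose. Refer to this from SAP 5.7.1.

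On the worked cases, the 25 October onset becomes 20 October. The −4 and −6 day durations each become 1 day; for the second, first dose is taken to be on or before 8 October. Bounding the stop by the start would not repair that second case, so the start must also be bounded by a known stop.

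Reconcile the rule with Protocol 12.1 and record the departure in SAP 5.9. The cost is a short SAP revision and a few program lines before database lock, with no effect on data collection or sample size.
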